## 1.0 Objectives / Specific Aims

### Specific Aim 1

The goal of Specific Aim 1 is to develop an effective remote mental health and substance use Screening, Brief Intervention and Referral to Treatment (SBIRT) program for pregnant and postpartum women. The **objectives** of this current application for Specific Aim 1 are to conduct a pilot RCT of a text-message based SBIRT and home-based telemedicine services for pregnant and postpartum women – called Listening to Women (LTW), compared to treatment as usual (TAU) with the primary objective to provide effect size estimates for a larger RCT.

**Specific Aim 1:** Conduct a pilot, small-scale randomized controlled trial to examine feasibility and preliminary efficacy of LTW, compared to TAU. Outcomes related to feasibility include percentage of eligible patients recruited, **study attrition**, **study retention**, and mental health and substance use treatment appointment attendance. Outcomes related to **preliminary efficacy** will include participation in screening, referral and treatment at baseline, compared to TAU.

The central hypotheses for Specific Aim 1 are that the study is feasible and women assigned to LTW will be more likely to screen positive and successfully obtain treatment in less time, compared to those that are assigned to TAU.

### Specific Aim 2

Upon completion of Specific Aim 1, the goal of Specific Aim 2 is to evaluate the effectiveness of a remote mental health and substance use Screening, Brief Intervention and Referral to Treatment (SBIRT) program for pregnant and postpartum women. The **objectives** of this current application for Specific Aim 2 are to conduct an RCT of a text-message based SBIRT and home-based telemedicine services for pregnant and postpartum women – called Listening to Women (LTW), compared to treatment as usual (TAU) with the primary objective to include attendance to treatment at baseline, compared to TAU.

**Specific Aim 2:** Conduct a randomized controlled trial to examine the effectiveness of LTW, compared to TAU. Outcomes related to **effectiveness** include attendance to treatment at baseline, compared to TAU.

The central hypotheses are that a greater proportion of women assigned to LTW will attend treatment following a referral, compared to TAU.

### Specific Aim 3

The goal of Specific Aim 3 is to gather data related to maternal and newborn diagnosis codes, health care utilization, and costs for our study participants with Medicaid.

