## 4.0 Study Endpoints

### Specific Aim 1:

#### **Primary pilot efficacy outcome variables include:**

Completion of SBIRT: We will compare the proportion of participants that complete a screen for mental health and substance use, the proportion of those screening positive that are referred to treatment, and the proportion of those referred to treatment that had at least one mental health and/or substance use disorder treatment appointment among those assigned to LTW, compared to TAU.

Time to Treatment: We will measure the time from completion of screening positive to time of first mental health or substance use treatment appointment (if a referral to treatment was appropriate) among those assigned to LTW, compared to TAU.

Reduction in Mental Health Symptoms: Among women referred for treatment, we will compare the mean change in the Edinburgh Postnatal Depression Scale (EPDS) among those assigned to LTW, compared to TAU. *Of note, the suicidal ideation question (item #10) will be omitted from this questionnaire.*

Reduction in Substance Use: Among women referred for treatment, we will compare change in substance use frequency and amount as measured by the NIDA-Modified Assist (see LTW protocol) among those assigned to LTW, compared to TAU.

Improved Maternal Functioning: Among women referred for treatment, we will compare the change in maternal functioning measured by the Medical Outcomes Study Short Form 36 (SF-36v2) among those assigned to LTW, compared to TAU.

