**Secondary Outcomes**

Reduction in Mental Health Symptoms: Among women referred for treatment, we will compare the mean change in the Edinburgh Postnatal Depression Scale (EPDS), GAD-7 Anxiety and CSSRS among those assigned to LTW, compared to TAU. *Of note, the suicidal ideation question (item #10) will be omitted from the EPDS questionnaire.*

Reduction in Substance Use: Among women referred for treatment, we will compare change in substance use frequency and amount as measured by the NIDA-Modified Assist (see LTW protocol) and TLFB among those assigned to LTW, compared to TAU.

Improved Maternal Functioning: Among women referred for treatment, we will compare the change in maternal functioning measured by the Medical Outcomes Study Short Form 36 (SF-36v2) among those assigned to LTW, compared to TAU.

Improved Health-Related Social Needs: Among women referred for treatment, we will compare the change in health-related social needs measured by the Accountable Health Communities (AHC) Health-Related Social Needs (HRSN) Screening Tool among those assigned to LTW, compared to TAU.

For the outcome variables for specific aims 1 and 2 we will collect data from the EHR including SBIRT data, if the participant was referred to treatment, where they were referred to treatment, if they attended a mental health or substance use treatment appointment and where they attended the appointment, how many appointments they attended, and the numbers of days from date of SBIRT completion to date of mental health or substance use treatment appointment.

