Statistical Analysis Plan

Sample Size and Power Analysis

Using a chi-square testing framework and a significance level of 0.05 and assuming two-sided hypothesis testing, both primary and secondary outcomes included a large enough sample size to detect differences between groups. Our a priori group sample sizes (usual care: n=191; LTWP: n=224) provided 80% power to detect between-group absolute differences in proportions ranging from 6% to 12% in the primary study outcomes (for example, screened: 65.2% [usual care] versus 77.7% [LTWP]; screened positive: 21.7% versus 34.2%, respectively; referred: 12.5% versus 23.1%, respectively; and attended treatment: 2.1% versus 8.3%, respectively). Our group sample sizes among participants completing a screen (usual care: n=63; LTWP: n=221) provided 80% power to detect between-group absolute differences in proportions ranging from 11% to 18% in the secondary study outcomes (for example, screened positive: 17.5% [usual care] versus 35.4% [LTWP]; referred: 3.2% versus 15.3%, respectively; and attended treatment: 1.6% versus 12.3%, respectively). The usual care rates used in these calculations were based on data published from earlier work on the LTWP program.

Data Analysis

We will assess the adequacy of randomization by comparing LTWP versus usual care (UC) on demographic, obstetric, and psychiatric baseline characteristics, using t-tests or Wilcoxon rank sum tests for continuous variables and chi-square tests or Fisher's exact tests for categorical variables, respectively. Descriptive statistics will be calculated for each screening method (LTWP versus usual care), including counts and percentages for participants who were screened, screened positive, referred to treatment, and attended treatment. Unadjusted differences in outcomes between people assigned to LTWP versus UC will be calculated using chi-square tests because all study outcomes are dichotomous. Relative risk (RR) ratios will be estimated and reported along with their 95% confidence intervals. All hypothesis tests will be two-sided with a type 1 error set at 0.05, and all analyses will be performed using SAS statistical software, version 9.4 (Cary, NC).

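### The SAP calls every outcome dichotomous, so Aim 1 time to treatment has no analysis, and as defined it compares groups formed after randomisation

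*SAP*

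**What the plan says.** Under Data Analysis, the SAP compares outcomes between arms by "chi-square tests because all study outcomes are dichotomous", with relative risks and 95% confidence intervals. Its t-tests and Wilcoxon tests are reserved for baseline characteristics. It gives no time-to-event method, time origin, censoring rule or rule for women who are never treated.

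The protocol differs on three counts:

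- Section 1.0 states the Aim 1 hypothesis that "women assigned to LTW will be more likely to screen positive and successfully obtain treatment in less time" than women in usual care.
- Section 4.0, under the Aim 1 heading "Primary pilot efficacy outcome variables include", defines Time to Treatment as "the time from completion of screening positive to time of first mental health or substance use treatment appointment", with the condition "if a referral to treatment was appropriate". The same list has changes in EPDS, substance use and SF-36, and the Aim 2 secondary outcomes repeat these.
- Section 4.0 also says the health record will supply "the numbers of days from date of SBIRT completion to date of mental health or substance use treatment appointment".

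Section 12.0 (Data Management and Analysis) refers back to an analysis plan earlier in the protocol. None appears in the protocol text supplied, so nothing there fills the gap.

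**The concern.** The reason given for using only chi-square tests is untrue for a primary pilot outcome and for several others. Chi-square tests and relative risks cannot analyse a duration, so half of the Aim 1 hypothesis has no planned analysis.

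Adding a method for the outcome as defined would not be enough. A woman enters the comparison only after a positive screen and a referral. Section 13.0 places the assigned intervention after randomisation, and section 3.0 says screening is by text in LTW and in person in usual care. The Aim 1 hypothesis itself predicts that LTW changes who screens positive. Women with a defined clock are therefore selected differently in the two arms. If text screening picks up women who are easier or harder to bring into care, the comparison of times shifts in either direction without any effect of LTW on speed. Since Aim 1 exists to supply effect sizes for a larger trial, a distorted estimate would be carried forward.

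**Working it through.** **1. Reproduce the SAP's own figure.** The SAP claims 80% power, two-sided 0.05, for 191 versus 224 women and for 63 versus 221 screen completers. Using the normal approximation with pooled null variance:

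power = Φ{[|p2 − p1| − 1.96·√(p̄(1−p̄)(1/n1+1/n2))] / √(p1(1−p1)/n1 + p2(1−p2)/n2)}

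For attendance (2.1% versus 8.3%), p̄ = (191×0.021 + 224×0.083)/415 = 0.0545, so power = Φ[(0.062 − 0.0438)/0.0212] = 80.5%. The other all-randomised examples give 80.6% (screened), 80.8% (positive) and 80.3% (referred). The completer examples give 80.2%, 80.4% and 80.4%. All seven reproduce. All seven are proportions; none concerns time.

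**2. Who enters the protocol's comparison.** Expected count = n × SAP rate. The pilot columns assume that 2:1 allocation of 100 gives 33 usual care and 67 LTW, and that the same rates apply.

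| Step | Usual care, 191 | LTW, 224 | Usual care, 33 | LTW, 67 |
|---|---|---|---|---|
| Positive (21.7% / 34.2%) | 41.4 | 76.6 | 7.2 | 22.9 |
| Referred (12.5% / 23.1%) | 23.9 | 51.7 | 4.1 | 15.5 |
| Attended (2.1% / 8.3%) | 4.0 | 18.6 | 0.7 | 5.6 |

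Referred women are 12.5% of one arm and 23.1% of the other. Censoring those not treated keeps them in the analysis, but it does not undo the unequal entry.

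**3. How thin the usual-care arm is.** At 2.1%, the chance that none of 33 usual-care women attends is 0.979^33 = 0.50, in which case a pilot hazard ratio cannot be estimated in the usual way. As a check, take the in-person rates in section 2.0 as nested (an assumption): 0.3333 × 0.5763 × 0.1604 = 3.1%, or 1.0 of 33 and 5.9 of 191; the chance of none in 33 is then 0.969^33 = 0.35.

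**4. What an all-randomised time analysis would offer.** Expected first visits are 4.0 + 18.6 = 22.6 in 415 women, and 0.7 + 5.6 = 6.3 in the pilot. Schoenfeld: power = Φ(√(d·π(1−π))·ln HR − 1.96), with π the LTW share. The hazard ratios are assumptions.

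| HR for starting treatment | 415 women (d = 22.6, π = 224/415) | Pilot (d = 6.3, π = 2/3) |
|---|---|---|
| 1.5 | 16% | – |
| 2 | 38% | 13% |
| 3 | 74% | 25% |
| 4 | 91% | 37% |

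Under proportional hazards, the SAP's attendance rates imply HR = ln(1−0.083)/ln(1−0.021) = 4.1.

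**The case against.** **The pilot defence.** Aim 1 is meant to estimate effect sizes, and time to treatment is neither a primary nor a secondary outcome of Aim 2. That is right, and it limits the consequence. It does not remove the need for a method that gives an interpretable estimate.

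**The analysis may include non-attenders.** A reader might infer that only attenders would be compared, about 4 against 19 women. No document says so. The definition sets a clock and a referred population, and untreated referred women could be censored, giving risk sets of about 24 and 52. This answers the charge of an attender-only analysis, but not the charge of selection after randomisation.

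**The LTW rates are not forecasts.** The SAP gives them as differences detectable with 80% power; only the usual-care rates are described as based on data. This stands. Taking the LTW rates in section 2.0 as nested gives 0.8115 × 0.7612 × 0.9491 = 58.6%, or 39 of 67 in the pilot instead of 5.6. The LTW counts are therefore very uncertain. The small usual-care count is not, and higher LTW rates would make entry more unequal.

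**Extreme selection.** A reader might divide the SAP's completer counts by its group sizes (63/191 = 33%, 221/224 = 99%) and infer that almost only LTW women are screened. The same paragraph gives 65.2% and 77.7% screened. The two pairs conflict, which is a separate matter, and the point here does not rely on the wider gap.

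**Changing the origin changes the question.** Counting from randomisation includes time before screening. No passage states that LTW aims to shorten that interval, so this is not a reason to prefer it. The reasons are that the section 1.0 hypothesis is not limited to time after screening, and that randomisation is the only origin shared by all women. With rare events the result will also overlap with the planned attendance comparison.

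**Conclusion.** The concern holds. The SAP's description of its outcomes is wrong for Time to Treatment and for the EPDS, substance-use and SF-36 changes, and no method for them appears in either document. For Time to Treatment, the protocol's definition leads to a non-randomised comparison, with about 24 versus 52 women referred at the SAP's illustrative rates. It would rest on about 4 treated usual-care women of 191, or about 1 of 33 in the pilot.

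These counts assume that the SAP rates apply and, for the pilot, a 33:67 split. The direction and size of any bias cannot be derived from the documents.

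A reader might go further and infer that the trial's main result is at risk. The documents do not support that: the Aim 2 primary outcome is attendance, a binary outcome, and the chi-square test and its stated power are sound for it.

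**What to change.** 1. Correct the SAP sentence so that it limits chi-square tests and relative risks to the binary outcomes. For the EPDS, substance-use and SF-36 changes, name a method or state that they will not be analysed.
2. For the hypothesis of faster treatment, define time from randomisation to first attended mental health or substance use treatment visit in all randomised women. Censor non-attenders at the end of a stated window; the span used for Aim 2 attendance, pregnancy through the first year postpartum, is one option.
3. Report cumulative incidence curves by arm and a hazard ratio with 95% CI. In the Aim 1 pilot, label this as estimation only, since about 6 events are expected at the SAP's illustrative rates, and say what is reported if an arm has no event.
4. Report days from screen to visit as description, without a between-arm test.

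The cost is small. A window and censoring rule must be written, allowing for unequal follow-up because women enrol both pregnant and postpartum. Appointment dates must be extracted, because days counted from SBIRT completion do not exist for women who were never screened.
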